The PrEvention of post-traumatic contractuRes with Ketotifen I (PERK-I) trial, a Phase II singlecenter randomized clinical trial (RCT) that compared oral Ketotifen Fumarate to a lactose placebo showed that Ketotifen Fumarate was neutral in terms of improving elbow range of motion (ROM)⁶. However, a subgroup of the trial, i.e., those who underwent surgery, indicated that Ketotifen Fumarate improved their range of motion. Therefore, the PrEvention of posttraumatic contractuRes with Ketotifen 2 (PERK-2) trial will assess the effectiveness of Ketotifen Fumarate in increasing the range of motion among surgical patients.

2. Study Objectives

The PERK-2 study aims to demonstrate that Ketotifen Fumarate (2 mg or 5 mg) administered within 10 days of injury is more effective than a placebo in reducing post-traumatic elbow joint contractures in adult participants with elbow fractures and/or dislocations. The efficacy of Ketotifen Fumarate over placebo will be assessed by comparing the difference in elbow range

Patient-Reported Outcome Measures (PROM). Lastly, the study will assess the safety of Ketotifen Fumarate through the reporting of adverse events (AE) and serious adverse events (SAE), fracture healing, and heterotopic ossification (HO) formation.

3. Study design

The PERK-2 trial is a phase III randomized controlled multicentre trial with three parallel groups. Eligible participants were assigned to receive Ketotifen Fumarate 2 mg, Ketotifen Fumarate 5 mg, or a lactose placebo in a 1:1:1 ratio. Eligible participants will be recruited at fifteen centers across North America.

3.1. Treatment Allocation/Randomization

Randomization will be centralized, secured, and concealed via a computer-generated randomization scheme to prevent allocation bias. The randomization criteria will be reviewed and approved by an independent Biostatistician. Screening, randomization, and enrolment will be organized through the Epidemiology Coordinating and Research Centre (EPICORE) at the University of Alberta. Eligible participants will be assigned to Ketotifen Fumarate 2 mg, Ketotifen Fumarate 5 mg, or lactose placebo in a 1:1:1 ratio. A computer generated randomization scheme stratified by site with block sizes of 3:6:9 will be used to assign eligible participants. The Investigators will have access to the randomizer (on REDCap) over the Internet via a desktop computer or a web-enabled smartphone.

3.2. Blinding/masking

The participants, investigators, and assessors will be blinded to the randomization groups. Blinding will be accomplished by over-encapsulating each medication, making Ketotifen Fumarate and placebo capsules appear indistinguishable. TEVA Canada provided the treatment (ketotifen). Also, Bay Area Research Logistics (BARL) Hamilton, ON Canada, a company that specializes in clinical trial medication packaging and distribution, did the over encapsulation by placing the appropriate number of ketotifen tablets or lactose placebo with the methyl cellulose so that the investigational product in each treatment arm looked identical. However, unblinding might happen whenever serious suspected adverse reactions.

Alberta Health

3.3. Concomitant Care

Participants will receive the following care while taking trial medication.

- a) Surgery: The participant and surgeon will determine the type of operation. This management is not randomly assigned and is determined by injury characteristics. The operation can be performed before or after randomization; randomization must occur within 10 days of injury.
- b) Medications: Analgesia can be provided by acetaminophen, opioids, and/or nonsteroidal anti-inflammatory drugs (NSAID) as required. The NSAIDs may have a confounding effect on the ROM measures by preventing HO following elbow injuries. Heterotopic ossification (HO) refers to bone formation in soft tissue. NSAIDs may be used in this trial as an analgesic at the discretion of the participant and surgeon because of the known analgesic benefits for

musculoskeletal injury and the ubiquitous accessibility to NSAIDs with non-prescription preparations.

lberta Health

c) Rehabilitation/Splints: If possible, at the site, a physiotherapist will direct a standardized home exercise program (HEP) for all groups. The HEP will consist of active ROM exercises for elbow extension-flexion arc and forearm pronation-supination arc performed 3x/day with 20 repetitions. Visits to the physiotherapist every 2 weeks will monitor progress and reinforce adherence to home therapy. Stretching splints will be used when physiotherapy alone is insufficient, which occurs at least 12 weeks post-randomization.

4. Sample Size Determination

The sample size was estimated using the Analysis of Covariance (ANCOVA) model using the mean difference of injured and contralateral elbow extension-flexion arc ROM at Week 12. The sample size was calculated based on a mean difference of 15° in the extension-flexion range of motion and a standard deviation of 45° between participants who received 2 mg or 5 mg Ketotifen Fumarate and those who received a placebo, using 95% power and a two-sided test at the 0.05 α -level. The sample size was recalculated due to COVID-19 (which temporarily impacted enrolment) and budgetary constraints. A total sample size of 381 participants (127 participants per arm) was determined to be adequate based on a mean change of 10° extension-flexion arc ROM from baseline to week 12 and a standard deviation of 25°, assuming an overall dropout rate of 11%. The standard deviation used was obtained from PERK-1 trial data. Following permission from Health Canada, the sample size was increased to 395.

5. Outcome measures

The primary endpoint examines whether at least one of the treatment arms (Ketotifen Fumarate 2 mg or 5 mg) is superior to placebo by comparing the mean difference in injured and contralateral elbow flexion-extension arc ROM at Week 12 (Table 1). The secondary endpoints will compare the mean change for multiple range of motion elements from Week 2 to other time points (Week 6, Week 12, Week 24, and Week 52) to establish Ketotifen Fumarate's efficacy over placebo. Other secondary endpoints will compare the mean difference in patients' reported outcome measures (PROMs) at multiple time points. Also, we will combined the two Ketotifen groups and compare it with placebo for the secondary endpoints. The safety assessment will compare the proportion of patients who experienced adverse effects (AEs), serious adverse effects (SAEs), suspected unexpected serious adverse reaction (SUSAR), nonunion and heterotopic ossification, and reoperation in each arm. Table 1 presents a summary of the study's objectives.

Table 1: Objectives and Endpoints

| Study Objectives | Endpoints | | | |
|---|--|--|--|--|
| | Primary | | | |
| Improvement in elbow range of motion. | The mean difference injured and contralateral elbow flexion-extension arc range of motion at Week 12. | | | |
| Socondary | | | | |
| Improvement in elbow range of motion (injured vs. contralateral elbow) at Week 12 | The mean difference injured and contralateral elbow at Week 12 for the following range of motion elements: i. Flexion ii. Pronation iii. Extension iv. Supination | | | |
| 2. Improvement in elbow range of motion from Week 2 to other timepoints | The mean changes from Week 2 to another timepoint (Week 6, Week 12, Week 24, and Week 52) for the following range of motion elements of the injured elbow:i.Flexion-extension arcii.Pronation- supination arciii.Flexioniv.Pronationv.Extensionvi.Supination | | | |
| 3. Improvement in health-related quality of life at Week 12 | The mean difference for the following health-related quality of life measures at Week 12 i. The Disability of the Arm, Shoulder, and Hand (DASH) ii. The Pain Catastrophizing Scale (PCS)) iii. The Oxford Elbow Score (OES) | | | |
| Improvement in health-related quality of life from Week 2 to other timepoints | Mean changes from Week 2 to another timepoint (Week 6, Week 12, Week 24, and Week 52) for the following health-related quality of life measures: | | | |

Alberta Health Services

| Study Objectives | Endpoints |
|------------------|---|
| | i. The Disability of the Arm, Shoulder, and Hand |
| | (DASH) |
| | ii. The Pain Catastrophizing Scale (PCS)) |
| | iii. The Oxford Elbow Score (OES) |
| 5. Safety | The proportion of SUSAR up till week 12 |
| | The proportion of fatal or life-threatening SAE up till week 12 |
| | The proportion of other SAE up till week 12 |
| | The proportion of composite reoperation for all elbow-related causes at week 12 |
| | The proportion of participants requiring reoperation for contracture at week 12 |
| | The proportion of SUSAR up till week 52 |
| | The proportion of fatal or life-threatening SAE up till week 52 |
| | The proportion of other SAE up till week 52 |
| | The proportion of composite reoperation for all elbow-related causes at week 52 |
| | The proportion of participants requiring reoperation for contracture at week 52 |

6. Analysis Set

a) Intent-to-Treat (ITT) Population: The primary endpoint analysis will be conducted on the ITT population, which includes all study participants and the treatment group to which they were assigned (i.e., the intended treatment). An ITT analysis will also be conducted for the secondary endpoints.

Alberta Health

- b) **Per Protocol (PP) Population:** The PP population includes all participants randomized and treated, with no major protocol deviations, including not meeting inclusion/exclusion criteria, not receiving the planned dose, receiving the incorrect study drug, or not obtaining consent (i.e., as treated). The primary analysis will be repeated on the PP population.
- c) **Safety Population:** The safety population comprises all participants receiving any amount of study drug. Participants will be analyzed based on the intervention they receive.

7. Statistical Analysis

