7.2. Primary, secondary, and safety analyses

The linear regression model will be used to model the mean differences in the range of motion as a function of the intervention received. The unadjusted model will use a univariate linear regression model to assess whether the participants' means of range of motion received Ketotifen Fumarate (2 mg or 5 mg) differed from those who received lactose placebo. A multivariate regression model will be used to adjust for the effect of baseline covariates, i.e., sex, age, side of injury is the same as the dominant hand, type of elbow injury, concurrent injury and site as a random variable. Type of elbow injury is defined as AO/OTA classification, i.e., distal humerus vs. proximal radius and ulna. Table 2 summarizes the statistical analyses.

Table 2: Statistical Analysis of Primary, Secondary, and Safety Endpoints

| Study Endpoint | Statistical Model | Estimate of treatment effects |
|--|--|---|
| | | |
| The mean difference between | Linear regression | The unadjusted mean difference |
| injured and contralateral elbow | This model will be used to obtain the unadjusted mean | and the corresponding 95% |
| flexion-extension at Week 12 | difference between the injured and contralateral elbow | confidence intervals |
| | flexion-extension at Week 12. | |
| | Secondary | |
| The mean difference between injured and contralateral flexion at Week 12 | The data will be analyzed with or without adjusting for specific baseline covariates. The statistical models are described below: a) Linear regression model This model will be used to obtain the unadjusted mean difference between injured and contralateral flexion at Week 12. b) The mixed-effects linear regression model This model will be used to obtain the adjusted mean difference between injured and contralateral flexion at Week 12. b) The mixed effects linear regression model This model will be used to obtain the adjusted mean difference between injured and contralateral flexion at Week 12. The baseline covariates sex, age, side of injury is the same as the dominant hand, type of elbow injury, and concurrent injury will be regarded as fixed variables, and site as a random variable. Type of elbow injury is defined as AO/OTA classification, i.e., distal humerus vs. proximal radius and ulna. | The mean difference and its corresponding 95% confidence intervals for both the unadjusted and adjusted analysis |

Alberta Health Services

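### Section 4 words the effect and SD behind the adopted sample size as a change from baseline, which is not the primary endpoint, and gives no power for that size

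*SAP*

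**What the plan says.** Section 4 opens with the sizing model: "The sample size was estimated using the Analysis of Covariance (ANCOVA) model". The variable named in that same sentence is the primary one: "using the mean difference of injured and contralateral elbow extension-flexion arc ROM at Week 12". It then gives a first set of inputs, 15° with an SD of 45°, "using 95% power and a two-sided test at the 0.05" level.

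Next it reports that the size was recalculated because of COVID-19 and budget limits. The adopted total of 381 (127 per arm) is "based on a mean change of 10° extension-flexion arc ROM from baseline to week 12 and a standard deviation of 25" degrees, with 11% overall dropout. On the source of the SD it adds only this: "The standard deviation used was obtained from PERK-1 trial data". The total was later raised to 395. No power or alpha accompanies 381 or 395.

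Section 5 sets the primary question as whether "at least one of the treatment arms (Ketotifen Fumarate 2 mg or 5 mg) is superior to placebo", judged by "comparing the mean difference in injured and contralateral elbow flexion-extension arc ROM at Week 12". The primary row of Table 2 uses linear regression without covariates: "This model will be used to obtain the unadjusted mean" difference on that variable. Change from Week 2 in the injured elbow appears in Section 5 and Table 1 as a secondary endpoint, and the ANCOVA rows of Table 2 label the Week 2 measurement the baseline value.

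**The concern.** The sentence that produces the adopted size names a different variable from the one the trial will test. A change from baseline in one elbow and a side-to-side difference at a single visit need not share an SD, and the SAP does not say which of them the PERK-1 figure of 25° describes. The sentence also does not say that 10° is a difference between arms, although the calculation needs it to be one.

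Separately, the one power figure in the section belongs to inputs that were replaced. A reader looking for the power of the trial finds 95% and nothing else.

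Two things are at stake: whether the size was justified on the primary endpoint, and what power should be quoted when the result is interpreted. The second matters most if the result is neutral.

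**Working it through.** **Inputs.** From SAP Section 4: difference 10°, SD 25°, dropout 11%, 381 in total (127 per arm), later 395. From Section 3.1: allocation 1:1:1. Two-sided alpha 0.05 is stated only with the superseded inputs and is carried forward here as an assumption. The 10° is taken as a between-arm difference, also an assumption.

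**Reproducing 381.** Evaluable per arm for two means: n = 2(z₀.₉₇₅ + z_power)² / d², with d = 10/25 = 0.4. Randomised per arm = n/0.89, rounded up. Total = three times that.

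| Power | n (formula) | Evaluable per arm | Randomised per arm | Total |
|---|---|---|---|---|
| 80% | 98.1 | 99 | 112 | 336 |
| 85% | 112.2 | 113 | 127 | **381** |
| 90% | 131.3 | 132 | 149 | 447 |
| 95% | 162.4 | 163 | 184 | 552 |

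Of these round values, only 85% returns 381 (113/0.89 = 126.97, so 127; 3 × 127 = 381). At 95%, one-sided 0.05 gives 153 per arm, two-sided 0.025 gives 213, and a three-group F test gives 165 to 220. None is 127.

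**Power per dose-placebo comparison at the adopted sizes** (noncentral t, d = 0.4):
- 381: 127 × 0.89 = 113 evaluable per arm, power 84.9%.
- 395: 395 × 0.89/3 = 117.2, so 117 evaluable per arm, power 86.1%.

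**Power for at least one dose** (simulation, pooled SD, each dose tested against placebo at an unadjusted 0.05):
- Both doses truly give 10°: 94.2% at 381 and 94.9% at 395.
- Only one dose gives 10°: 85.1% at 381 and 86.2% at 395.

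**Sensitivity to the SD.** With 117 per arm, 80% power needs d = 0.368, so 10° is detectable at 80% only up to an SD of 10/0.368 = 27.2°. The SAP gives no other SD for the adopted calculation, so the next two values are assumptions: power per comparison is about 72% at 30° and about 59% at 35°.

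**The case against.** The strongest reply is that nothing in Section 4 is arithmetically false. The 95% is printed beside 15° and 45°, the text then says the size was recalculated, and it never claims 95% for 381 or 395. The first sentence of the section names the primary variable, so the change-from-baseline phrase may be no more than loose wording. Much of this stands. A reader might infer that the SAP claims 95% power for the current design; it does not say so. The fault is that the only figure on record belongs to a replaced calculation.

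A reader might also infer that the trial is underpowered. The documents do not support that: if 25° is the SD of the primary variable, 85% to 86% per comparison is a sound design.

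Nor do they support treating 25° as a covariate-adjusted SD because Section 4 mentions ANCOVA. The figure gives 381 directly in the plain two-sample formula, with no reduction for a covariate, so ANCOVA looks like a label that does not match the primary row of Table 2.

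The sponsor could also say that power for at least one dose, the stated objective, is about 95%. That is true only if both doses give the full 10° and each is tested unadjusted at 0.05. The SAP states neither this definition of power nor its assumption.

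One thing the reply does not remove: the sentence behind the adopted size contradicts the section's own first sentence and the primary endpoint, and the SAP does not settle which was meant.

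**Conclusion.** The point holds as an internal inconsistency that should be fixed. The effect and SD behind the adopted size are worded on a variable that is not the primary endpoint, and no power is stated for that size.

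The adopted inputs imply 85% per dose-placebo comparison at 381 and about 86% at 395, against 552 participants for 95%. The 85% is back-solved. It rests on two-sided 0.05 carrying over and on 10° being a between-arm difference, and the sponsor must confirm it.

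The conflict in wording is certain; its effect on power is conditional. If 25° is the PERK-1 SD of the injured-contralateral Week 12 difference, only the text changes. If it is the SD of something else, the SAP does not allow the power for the primary endpoint to be worked out.

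**What to change.** In Section 4:

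1. Check which PERK-1 variable gave 25°. If it is the injured-contralateral arc difference at Week 12, restate 10° and 25° as the between-arm difference and SD of that variable and drop the change-from-baseline wording.
2. If it is not, give the PERK-1 SD of the primary variable and the resulting power, or the detectable difference, at 395.
3. Align the ANCOVA label with the unadjusted primary model in Table 2.
4. Mark 95% as belonging to the superseded calculation. Once 25° and the carried-over alpha are confirmed, state about 86% per dose-placebo comparison at 395 and two-sided 0.05.
5. If power for at least one dose is quoted, give its assumption: about 95% only if both doses give 10° and each is tested unadjusted at 0.05, about 86% if only one does.

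The cost is one look at the PERK-1 data and a few sentences. The sample size, test and estimate do not change. The small downside is that the power on record will be less favourable than the only figure now printed.

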7.1. Descriptive Analysis

Continuous endpoints will be summarized using means, standard deviation, medians, and interquartile ranges. The differences among groups will be compared using Kruskal-Wallis's test. Categorical endpoints will be summarized using frequency and proportion. Chi-square tests will be used to compare categorical endpoints. Point estimates with two-sided 95% confidence intervals will be produced for group differences. These endpoints, baseline covariate, and stratification factors used during randomization will be summarized by treatment intervention

for the ITT population. Similar analyses will be conducted for the PP population and safety population.

Alberta Health

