| from Week 2 to Week 52 | a) Analysis of Covariance (ANCOVA) This model will be used to assess the mean difference in OES score between Week 2 and Week 52 among the treatment groups after adjusting for OES score at Week 2 (baseline value). The model will have Dependent variable: The OES score at Week 52 Independent variable: Treatment group Covariate: OES score at Week 2, sex, age, side of injury is the same as the dominant hand, type of elbow injury, and concurrent injury will be regarded as fixed variables, and site as a random variable. Type of elbow injury is defined as AO/OTA classification, i.e., distal humerus vs. proximal radius and ulna. b) Mixed-effects linear regression model This model will be used to account for correlation among observations and estimate the effect of covariates on repeated outcomes. It will use the OES score recorded at the time points. Also, the baseline covariates sex, age, side of injury is the same as the dominant hand, type of elbow injury, and concurrent injury will be regarded as fixed variables, and site as a random variable. Type of elbow injury is defined as | Mixed-effect linear regression model: The mean difference and its corresponding 95% confidence intervals |
| | injury will be regarded as fixed variables, and site as a random variable. Type of elbow injury is defined as AO/OTA classification, i.e., distal humerus vs. proximal radius and ulna. | |

| Study Endpoint | Statistical Model | Estimate of treatment effects |
|---|---|--|
| | Safety | |
| Suspected unexpected Serious Adverse Reaction (SUSAR) up to Week 12 | The analyses will be unadjusted to avoid estimates with wide confidence intervals since we expected that the event rate might be low and that this is likely no event in some treatment groups. | Odds ratio and p-value for both the omnibus and pairwise differences models. |
| | Fisher's exact test The test will be used to compare the proportion of SUSAR up to Week 12 in the treatment groups. If the test produces a significant p-value at α = 0.05, a post-hoc test will be performed to identify groups that | |
| | differ. The p-values will be corrected using the Benjamin- Hochberg FDR method to ensure that the family-wise Type I error remains at 0.05. | |

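### The primary claim succeeds if either dose beats placebo but has no multiplicity rule; one 0.05 test per dose would raise false superiority from 2.5% to about 4.5%

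*SAP*

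**What the plan says.** Section 5 (Outcome measures) sets the primary criterion: "The primary endpoint examines whether at least one of the treatment arms (Ketotifen Fumarate 2 mg or 5 mg) is superior to placebo". The measure is the week 12 difference between the injured and the contralateral flexion-extension arc.

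Section 4 (Sample Size Determination) gives the only significance level tied to this endpoint, in its first calculation (15°, SD 45°): "using 95% power and a two-sided test at the 0.05" level. It then reports a recalculation with 10°, SD 25° and 11% dropout: "A total sample size of 381 participants (127 participants per arm) was determined to be adequate". The size was later raised to 395. No power is given for either 381 or 395.

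Section 7.2 uses linear regression to ask whether the means of those who "received Ketotifen Fumarate (2 mg or 5 mg) differed from those who received lactose placebo". The primary row of Table 2 asks for the unadjusted mean difference with a 95% confidence interval. Section 7.1, on descriptive analysis, adds that "Point estimates with two-sided 95% confidence intervals will be produced for group differences" and names a Kruskal-Wallis test, which gates nothing.

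The safety rows of Table 2 are handled differently. Each begins with a three-group Fisher test at 0.05. Only if that is significant does the plan say "a post-hoc test will be performed to identify groups that" differ, and the p-values are then corrected with the Benjamini-"Hochberg FDR method to ensure that the family-wise Type I error remains at 0.05". No primary or secondary efficacy row has such a rule. Section 5 plans to pool the two doses for secondary endpoints only.

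**The concern.** An at-least-one criterion is a union of two claims, so its error rate is the chance that either comparison gives a false positive. A 0.05 level for each comparison does not hold that chance at 0.05. The SAP itself joins the two doses into one claim, so they cannot be treated as separate questions that each carry their own 5%.

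The plan controls error across arms within each safety endpoint but not where the confirmatory efficacy claim is made. Two things are at stake in this phase III trial. On the natural reading, an ineffective drug would be declared superior nearly twice as often as the stated level suggests. And because the rule is unwritten, a correction, or none, could be chosen with the results in view.

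**Working it through.** **Inputs from the SAP.** Two dose-versus-placebo comparisons, either of which suffices (Section 5). Two-sided 0.05 (Section 4). Allocation 1:1:1 (Section 3.1), so the two test statistics share the placebo arm and have correlation 0.5. Difference 10°, SD 25°, dropout 11%, 127 per arm, later 395 in total (Section 4). I assume no gain in precision from covariates.

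**1. The plan's own sample size.** The power behind the recalculation is not stated, so I tried several values with n = 2[(25/10)(z₀.₉₇₅ + z_power)]² per arm, divided by 0.89.

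| Assumed power | Two-sided 0.05 per dose | Bonferroni, two-sided 0.025 per dose |
|---|---|---|
| 80% | 99 → 112 | 119 → 134 |
| 85% | 113 → **127** | 135 → 152 |
| 90% | 132 → 149 | 156 → 176 |
| 95% | 163 → 184 | 189 → 213 |

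(The right-hand column uses z₀.₉₈₇₅.) The figure of 127 is matched by an uncorrected 0.05 per dose with an assumed 85% power, and by no Bonferroni variant shown. This supports the uncorrected reading but does not prove it.

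**2. Error when both doses are null.** For (Z₁, Z₂) bivariate normal with correlation 0.5:

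- Two-sided family-wise error: 1 − P(|Z₁| < 1.96, |Z₂| < 1.96) = 0.0907, against 0.05 for a single test.
- False superiority of at least one dose: 1 − P(Z₁ < 1.96, Z₂ < 1.96) = 0.0454, against 0.025.

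A simulation with t tests at 113 per arm gives 9.0% and 4.5%.

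**3. Error under rules that control it.** Dunnett's critical value solves P(|Z₁| < c, |Z₂| < c) = 0.95, which gives c = 2.212, or 0.0270 per comparison. The two errors return to 5.0% and 2.5%. Bonferroni gives 4.65% and 2.32%. A 5% omnibus F test followed by pairwise tests at 0.05 gives about 4.2% and 2.1% by simulation.

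**4. Power.** Evaluable per arm: 127 × 0.89 = 113 and 395 × 0.89 / 3 = 117. The non-centrality is 0.4 × √(n/2), which is 3.007 and 3.059.

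| | n = 113 (381) | n = 117 (395) |
|---|---|---|
| Per dose, uncorrected: Φ(ncp − 1.96) | 85.2% | 86.4% |
| Per dose, Dunnett: Φ(ncp − 2.212) | 78.7% | 80.2% |
| At least one, both doses give 10°, uncorrected | 94.4% | 95.0% |
| At least one, both doses give 10°, Dunnett | 90.4% | 91.4% |
| At least one, only one dose gives 10°, Dunnett | 78.7% | 80.2% |

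The omnibus gate at 113 per arm has 82% power if one dose works and 88% for at least one if both work (simulation).

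**5. Intervals at 113 per arm.** SE = 25 × √(2/113) = 3.33°. Half-widths are 1.96 × 3.33 = 6.5° (ordinary) and 2.212 × 3.33 = 7.4° (simultaneous). The ratio is 2.212/1.96 = 1.13.

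**The case against.** The best counter-argument is that the SAP is silent on the rule, so it does not commit to two tests at 0.05. Table 2 asks for an estimate and an interval, not a p-value. Section 4 speaks of one test. A three-arm regression also yields an omnibus test, and omnibus-then-pairwise is the pattern used for every safety endpoint. Under that pattern the error is about 4.2% and nothing is inflated.

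This stands in part: the 4.5% and 9.1% hold only if each dose is tested at 0.05. But the SAP attaches no gate to the primary endpoint, the Kruskal-Wallis test is descriptive, and the criterion, the single 0.05 and the plain 95% intervals all point to uncorrected comparisons. If the rule really is open, that is itself a defect in a confirmatory analysis.

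Three smaller points are fair:

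- Section 7.3 also sets a level of 0.05, but for exploratory subgroup analyses, so it does not bear on the primary claim.
- The sample-size match rests on an assumed 85% power.
- Dunnett's single-step procedure is not the only sound choice. Holm, a fixed sequence or step-down Dunnett would also control the error. Step-down Dunnett has about 83% power per dose when both doses work at 113 per arm, against 79% for single-step. Its drawback is that intervals matching the tests are less simple.

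**Conclusion.** The concern holds and must be fixed. The SAP makes an at-least-one-dose claim without any rule that controls error across the two doses. With one two-sided 0.05 test per dose, false superiority would be 4.5% instead of 2.5% and two-sided family-wise error 9.1% instead of 5%. These figures assume that both doses are null, that arms are equal in size and that the placebo arm is shared. They do not depend on the effect size or the SD. That no rule is stated is certain; the amount of inflation is conditional on the uncorrected reading.

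**What to change.** In Sections 5 and 7.2, state that 2 mg and 5 mg are each compared with placebo from one three-arm linear model, using Dunnett's procedure at family-wise two-sided 0.05. Success is at least one Dunnett-adjusted p-value below 0.05 in favour of ketotifen. In the primary row of Table 2, replace the ordinary intervals with simultaneous 95% intervals. In Section 4, state the power of the recalculated size under that rule: about 79% per dose at 381 and 80% at 395, and about 90% and 91% for at least one dose if both give 10°.

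The change is SAP wording and needs no extra patients, but it must be made before unblinding; the SAP does not say whether that has happened. Power per dose falls by about 6 points and intervals widen by about 13%. Restoring 85% per dose would take 149 per arm (447 in total), which the recommendation does not require. Compared with a safety-style omnibus gate, Dunnett has slightly less power if only one dose works (79% against 82%), slightly more for at least one if both work (90% against 88%), and gives intervals that agree with the tests. If the sponsor prefers another procedure that controls the error, it should be named at the same point, with its power.
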